6.5 Dose Modification

Not applicable. Subjects in Cohort 2 will be administered a single dose of Abilify MyCite at the same dose as their currently prescribed aripiprazole dose.

6.6 Prior/Concomitant Medications or Therapies

The investigator will record all medications (including, but not limited to, prescription medications, over-the-counter medications, vitamins, herbal remedies, etc) and therapies taken by the subject from 7 days prior to D-Tect Patch application through the end of the evaluation period (defined as the time period during which subjects are evaluated for primary and/or secondary objectives) in the eCRF. The investigator will also record all medications and therapies taken by the subject for treatment of an AE or which caused an AE until the end of the trial (defined as the last date of contact or date of final contact attempt) in the eCRF.

6.7 Intervention After the End of the Trial

Not applicable.

Confidential - Proprietary Information

27

7 Discontinuation of Trial/Treatment and Subject Discontinuation/Withdrawal

7.1 Entire Trial or Treatment

If the sponsor terminates or suspends the trial for any reason, prompt notification will be given to investigators, institutional review boards (IRB), and regulatory authorities in accordance with regulatory requirements.

7.2 Individual Site Discontinuation

Individual trial site participation may be discontinued by the sponsor, the investigator, or the IRB if judged to be necessary for medical, safety, regulatory, ethical or other reasons consistent with applicable laws, regulations, and Good Clinical Practice (GCP). The investigator will notify the sponsor promptly if the investigator or the IRB at the site discontinues participation in the trial.

7.3 Discontinuation of Trial Device

Under certain circumstances, it may be necessary for a subject to permanently discontinue the trial. If trial IEMs or patches are permanently discontinued, the subject should, if at all possible, remain in the trial to be evaluated for safety assessments. See the schedule of assessments (SoA) for data to be collected at the time of discontinuation of trial device and follow-up and for any further evaluations that need to be completed. If a subject discontinues the trial due to an AE, the investigator, or other trial personnel, will make every effort to follow the event until it has resolved or stabilized.

For each subject who discontinues the trial, the main reason for discontinuation will be recorded in the eCRF (refer to Section 7.4.1).

7.3.1 Interruption of Trial Procedures

If a subject temporarily interrupts trial device use due to an AE, the investigator, or other trial personnel, will make every effort to follow the event until it has resolved or stabilized. For each subject who has an interruption in trial device use, the main reason for interruption will be recorded in the eCRF.

7.4 Subject Discontinuation/Withdrawal from the Trial

- A subject may withdraw from the trial at any time at the subject's own request for any reason (or without providing any reason).
- A subject may be withdrawn at any time at the discretion of the investigator for safety, behavioral, or compliance reasons.

Confidential - Proprietary Information

28

- At the time of discontinuing from the trial, if possible, an early discontinuation visit should be conducted to assess any new or ongoing AEs.
- If a subject withdraws consent from the trial, the subject will be permanently discontinued from all trial procedures and the trial.
- If the subject withdraws consent for disclosure of future information, the sponsor may retain and continue to use any data collected before the withdrawal of consent.

Complete withdrawal of consent requires a subject's refusal of ALL of the following methods of follow-up:

- Participation in all follow-up procedures specified in the protocol (whether in-clinic, by telephone, or by a home visit).
- Participation in a subset of protocol-specified follow-up procedures (by a frequency schedule and method, as agreed by subject and trial site staff).
- Contact of the subject by trial site staff, even if only by telephone, to assess current medical condition, and obtain necessary medical reports relevant to the trial's objectives.
- Contact of alternative person(s) who have been designated in source records as being available to discuss the subject's medical condition, even if only by telephone, mail, or email (eg, family, spouse, partner, legal representative, friend, neighbor, or physician).
- Access to medical information from alternative sources (eg, hospital/clinic medical records, referring doctor's notes, public records, dialysis, transplantation or vital registries, social media sources).

Withdrawal of consent is a critical trial event and, therefore, should be approached with the same degree of importance and care as is used in initially obtaining informed consent. The reasons for a subject's intended withdrawal need to be completely understood, documented, and managed to protect the rights of the subject and the integrity of the trial. Only subjects who withdraw their permission for all of the above methods of follow-up are considered to have completely withdrawn their consent to participate in the trial.

7.4.1 Documenting Reasons for Subject Discontinuation/Withdrawal

A subject may discontinue the trial or withdraw from the trial for the reasons listed below:

- Adverse event
 - Continuing investigational device and/or ingestion of IEMs (MITs and/or Abilify MyCite) places the subject at undue risk as determined by the investigator (eg, a safety concern that is possibly, probably, or likely related to the investigational device or its components)
 - Serious adverse event (SAE)
 - Other potentially investigational device-related safety concerns or AEs

Confidential - Proprietary Information

29

Approval: 18 Apr 2023

Until the information herein is released by Otsuka to the public domain, the contents of this document are Otsuka confidential information and should not be duplicated or re-distributed without prior written consent of Otsuka.

- Death
- Lost to follow-up
- Physician decision
- Pregnancy
- Protocol deviation
- Protocol-specific withdrawal criterion met
- Site terminated by sponsor
- Withdrawal by subject

7.5 Lost to Follow-up

Subjects who cannot be contacted on or before Visit 3 (Day 8 [+ 2 days]) during the trial period, who do not have a known reason for discontinuation (eg, withdrew consent or AE), and for whom a survival status at the end of the trial cannot be determined will be classified as "lost to follow-up."

The site will make 3 documented attempts to contact the subject by telephone and in the event the site is unable to reach the subject by telephone, the site will attempt to contact the subject via certified mail or an alternative similar method, where appropriate, before assigning a "lost to follow-up" status.

If the subject was classified as "lost to follow-up," the following information will be recorded in the eCRF: "Date of final contact attempt" and "Contact method."

8 Trial Procedures

This trial consists of up to 3 days of onsite testing activities, including the screening visit, testing visit (conducted either on the same day as Visit 1 or up to 7 days after Visit 1), and the in-person safety follow-up visit, which will occur on Day 8 (+ 2 days). The D-Tect Patch will be worn until the in-person follow-up visit. Consent will be obtained from subjects prior to conduct of any testing related assessments or procedures in a manner consistent with GCP.

The assessments to be conducted during the trial are summarized in Table 1.3-1.

Screening

The informed consent process will be administered at Visit 1. The investigator (or designee) will determine whether a subject meets all eligibility criteria. In addition to gathering information specifically pertaining to the eligibility criteria, the investigator (or designee) will conduct a brief health screen. Only responses related to the eligibility criteria will be recorded in the eCRF. The investigator (or designee) will include this assessment in determining whether the level of risk for an individual is acceptable for

Confidential - Proprietary Information

participating in testing and will record whether the risk is acceptable on the appropriate screening eCRF. All recorded information will be de-identified. A physical examination is not required to be performed as part of screening, although evaluation of any subsequent AEs may require a targeted exam by a member of the clinical staff. Subjects will be instructed not to take their prescribed dose of aripiprazole on Day 1 of the trial.

Testing Visit

The research staff will meet with subjects for activities specified in Table 1.3-1 including assessment of AEs, review of concomitant medications, preparation of skin for patch placement, patch placement and photographs, DOI(s), and administration of the Sleep Diary. Subjects' food and drink intake on the Testing Day will be recorded by clinic staff.

Trained research staff will prepare subject skin to ensure good patch adhesion and place the D-Tect Patch on the subject. Skin preparation techniques may include cleansing of the skin with the provided "Simple" brand wipes, and/or clipping or shaving of excessive hair. To place the D-Tect Patch, the subject will be required to temporarily shift their shirt (and undergarments, if applicable) to allow access to the upper body. Even numbered subjects will have one D-Tect Patch placed on the right costal margin, anywhere from the xiphoid to the right mid-axillary line. Odd numbered subjects will have one D-Tect Patch on the left costal margin, anywhere from the xiphoid to the left mid-axillary line as shown in Figure 8-1.

Confidential - Proprietary Information

31

Approval: 18 Apr 2023

Until the information herein is released by Otsuka to the public domain, the contents of this document are Otsuka confidential information and should not be duplicated or re-distributed without prior written consent of Otsuka.

After the D-Tect Patch is successfully placed, the subject can readjust their clothes. Staff will confirm that no patch placed comes into contact with the wire within a bra (where applicable). Non-site trial staff may perform quality control (QC) of patch placement on subjects. Patch placement photographic evidence will be documented. A minimum of 3 patch placement photos is required:

- 1) Prior to initial dose
- 2) After completion of the 15th MIT dose (Cohort 1) or after completion of the single dose of Abilify MyCite (Cohort 2)
- 3) When the subject returns for follow-up prior to removing the patch

One day of DOIs is planned for this trial. Subjects will ingest tablets per the dosing outlined in Table 8-1 below. For subjects in Cohort 2, site staff will confirm that subjects did not take their prescribed dose of aripiprazole at home prior to the DOI of Abilify MyCite. Subjects will ingest tablets with approximately 60 mL of bottled water. The tablets will be administered by research staff and staff members will observe and record the timing of the individual ingestion events on the DOI eCRF. Site staff will conduct mouth checks and also verify checking after a subject swallows each tablet.

| Table 8-1 | Dosing Schedule | | |
|-----------|--|--|-------|
| Cohort | Ingestions/Session | Time Between Dosing Sessions (minutes) | Visit |
| Cohort 1 | One IEM tablet (MIT dose form) / 15 times | Approximately every 15 (-5 / +15) minutes | 2 |
| Cohort 2 | Single dose of Abilify MyCite / 1 time | Not applicable | 2 |

For any subject where tablet registration is missing, the trial team will consider execution of additional trial parameters including, but not limited to the following: ruling out bad patch impedance (eg, patch is not adhering to the skin properly) that can be addressed by changing the patch, potential contamination of the placebo tablets by introducing a new, sealed bottle of placebo tablets, and removing the DMS from the patient and having a non-site related, sponsor representative test the system independent of the subject to rule out unexplained subject anomalies (eg, medical or unknown conditions that may prevent patch registration of the ingested tablet). Any parameters executed may necessitate additional subject enrollment to replace missing ingestions during trial testing.

Subjects will be sent home with a Sleep Diary to complete each day until they return for the follow-up visit on Day 8 [+ 2 days]. Instructions on how to complete the sleep diary will be provided to the subject by the trial staff.

Follow-up Visit

All patches will be removed by trial staff at the in-person follow-up visit if the patch is still adhered on Day 8 [+ 2 days]. Any patch that peels off during the trial should be retained by the subject and given to trial staff during the scheduled in-person follow-up visit. If an in-person follow-up visit cannot occur, the site should conduct a telephone follow-up visit to assess safety and instruct the subject to remove the patch on Day 8. If the in-person follow-up visit is delayed past Day 8, subjects should be instructed to remove the patch on Day 8 and retain the patch to be given to site staff the in-person follow-up visit.

Subjects will return the completed Sleep Diary to trial staff at this visit.

At the in-person safety follow-up visit, information regarding AEs that may have occurred during or since Visit 2 will be elicited. Any ongoing AE associated with the use of the device or IEMs at the in-person follow-up visit should be followed to resolution per the judgment of the investigator unless the subject is lost to follow-up. If an in-person follow-up visit cannot occur, the site should conduct a telephone follow-up visit and verbally assess subject safety.

Responsibilities for Testing Subjects

- Wear the D-Tect Patch on the torso during the Testing Day and leave the patch on the torso until the in-person follow-up visit or the patch falls off.
- Complete a Sleep Diary each day until the in-person follow-up visit.
- Direct observed ingestions:
 - Cohort 1: Swallow 15 MITs in a single calendar day.
 - Cohort 2: Swallow a single dose of Abilify MyCite in a single calendar day at the same dose as subject's aripiprazole prescription.
- Subjects must be comfortable reporting any AEs (Section 8.7).
- Participate in all onsite visits and procedures.
- Participate in an in-person safety follow-up site visit approximately 7 days (+ 2 days) after applying the D-Tect Patch. All patches will remain on the torso until removed by trial staff at the in-person follow-up visit on Day 8. If a patch falls of early, the subject should retain the patch and return it to site staff at their scheduled in-person follow-up visit.

8.1 Efficacy Assessments

Not applicable.

8.2 Pharmacokinetic Assessments

Not applicable.

Confidential - Proprietary Information

33

8.3 Biomarker Assessments

8.3.1 Pharmacodynamic Assessments

Not applicable.

8.4 Pharmacogenomic Assessments

Not applicable.

8.5 Future Biospecimen Research Samples

Not applicable.

8.6 Safety Assessments

Reporting of AEs associated with the use of the device or ingestion of IEMs (MITs or Abilify MyCite) will occur during active testing participation. AEs will be triaged and assessed as appropriate (Section 8.7).

Details pertaining to the definitions, collection, reporting, and follow-up of AEs are described in Section 8.7.

8.6.1 Skin Irritation Scoring System

If an AE is related to the patch, then the Skin Irritation Scoring System (Table 8.6.1-1) will be completed by the investigator.¹ A photo of the affected area should also be taken. Patch-related AEs Grade 2 or above will be considered clinically significant for purposes of this trial and must be recorded on the safety reporting form and on the eCRF.

| Table 8.6.1-1 | Skin Irritation Scoring System |
|---------------|---|
| Grade | Skin Event |
| 0 | No evidence of irritation |
| 1 | Minimal erythema, barely perceptible |
| 2 | Definite erythema, readily visible; minimal edema or minimal papular response |
| 3 | Erythema and papules |
| 4 | Definite edema |
| 5 | Erythema, edema, and papules |
| 6 | Vesicular eruption |
| 7 | Strong reaction spreading beyond the test site |

Source: United States (US) Department of Health and Human Services, Food and Drug Administration

Center for Drug Evaluation and Research, December 1999.¹

8.6.2 Clinical Laboratory Assessments

Not applicable.

Confidential - Proprietary Information

34

8.6.3 Physical Examination

A physical examination is not required to be performed as part of screening, although evaluation of any subsequent AEs may require a targeted exam by a member of the clinical staff.

8.6.4 Vital Signs

Vital signs will be collected at the time point described in the schedule of assessments (Section 1.3). Subject vital signs should be monitored and assessed for potential clinical significance.

8.6.5 Electrocardiogram

Not applicable.

8.7 Adverse Events

8.7.1 Definitions

- Adverse Event (AE): any untoward medical occurrence, unintended disease or injury, or untoward clinical signs (including abnormal laboratory findings) in subjects, users or other persons, whether or not related to the investigational medical device or IEMs (MITs and/or Abilify MyCite) and whether anticipated or unanticipated.²
- Serious adverse event (SAE): AE that led to any of the following:
 - Death
 - Serious deterioration in the health of the subject, users, or other persons as defined by one or more of the following:
 - A life-threatening illness or injury
 - A permanent impairment of a body structure or a body function including chronic diseases
 - Inpatient or prolonged hospitalization
 - Planned hospitalization for a pre-existing condition, or a procedure required by the clinical investigation plan, without serious deterioration in health, is not considered an SAE
 - Medical or surgical intervention to prevent life-threatening illness or injury, or permanent impairment to a body structure or a body function
 - Fetal distress, fetal death, a congenital abnormality, or birth defect including physical or mental impairment
 - Nonserious AEs: all AEs that do not meet the definition of an SAE are considered nonserious AEs.
- Immediately Reportable Event (IRE):
 - Any SAE.

Confidential - Proprietary Information

35

Severity: Adverse events will be graded on a 3-point scale and reported as indicated in the eCRF. The severity of an adverse experience is defined as follows:

| 1 = Mild: | Discomfort noticed, but no disruption to daily activity. |
|---------------|--|
| 2 = Moderate: | Discomfort sufficient to reduce or affect normal daily activity. |
| 3 = Severe: | Inability to work or perform normal daily activity. |

Causality: Assessment of causal relationship of an AE to the use of the patch, MITs, and/or Abilify MyCite is defined as follows:

| Related: | There is a reasonable possibility of a temporal and causal relationship between the patch, MITs, and/or Abilify MyCite and the AE. |
|--------------|--|
| Not Related: | There is no temporal or causal relationship between the patch, MITs, and/or Abilify MyCite and the AE. |

8.7.2 Eliciting and Reporting Adverse Events

The investigator will periodically assess subjects for the occurrence of AEs (serious and nonserious, associated with the use of the patch, MITs, and/or Abilify MyCite) from the time the ICF is signed until the end of the trial. For this trial, information on AEs will be followed until resolution as determined by the investigator. All patches will be removed by trial staff at the in-person follow-up visit. Any patch that peels off during the trial should be retained by the subject and given to trial staff at the scheduled in-person follow-up visit.

To avoid bias in eliciting AEs, subjects should be asked the nonleading question: "How have you felt since your last visit?" All AEs (serious and nonserious) must be collected. All SAEs must be reported within 24 hours of awareness, no later than 72 hours in the case of a weekend or holiday. If a patch-related AE is reported by the subject, it will be graded per Section 8.6.1. A full list of all reported events will be kept by the clinical research site.

For this trial, all IREs (SAEs) detected during the program must be reported to:

- [contact]
- (fax) [contact]

Reconciliation of AEs reported in this trial will be performed at the end of the trial.

8.7.3 Immediately Reportable Events

The investigator must immediately report (within 24 hours), using an IRE form, after he/she or site personnel become aware of any IRE (SAE), by telephone, fax, or e-mail to

Confidential - Proprietary Information

36
the sponsor or designee using the contact information on the cover page of this protocol (please note that the IRE form is NOT the AE eCRF). Patient confidentiality must be protected and contact information such as name, address, phone number or any other protected health information as determined by applicable local regulation must be redacted when forwarding Safety Information and supporting documentation. Details regarding the follow-up of IREs are included in Section 8.7.7.2.

8.7.4 Medical Device Incidents (Including Malfunctions)

Not applicable.

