6.2.5 Reporting of Product Quality Complaints

Product Quality Complaints (PQCs) will be reported for Abilify MyCite tablets only. PQCs will not be reported for the D-Tect Prototype Patch, MIT dose form, or app.

A PQC is any written, electronic, or oral communication provided by a healthcare professional, consumer, clinical trial subject, medical representative, regulatory agency, partner, or other third party that alleges deficiencies related to the identity, quality, durability, reliability, safety, effectiveness, or performance of a medical device or

medicinal product or a falsified, tampered, or diverted product after it is released for distribution.

Examples include, but are not limited to, communications involving:

- Failure of a product to meet any of its specifications.
- Incorrect or missing labeling.
- Packaging issues: (eg, damaged, dirty, crushed, missing tablet, missing patch/pod, missing component).
- Tablet/bottle defects: (eg, odor, under-filled bottle, empty bottle, over-filled bottle, tablet not registering with the app, chipped tablet, broken tablet).
- Loss or theft of product.

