9.3 Handling of Missing Data for Primary and Secondary Endpoint Analysis

Missing data on PDA and/or detection latency measures will not be imputed.

9.4 **Statistical Analyses**

9.4.1 **Primary Endpoints**

The number of positive detections and PDA will be summarized for the D-Tect Patch for Cohort 1; the 95% CI of PDA will be provided using the Clopper-Pearson method. PDA is defined as PDA = $k \div n$, where n is the number of the total DOIs, and k is the number of positive detections by the patch.

For detection latency, summary statistics will be provided for Patch Detection Latency, Ingestion Data Transfer Latency, and Total Detection Latency. Kaplan-Meier curves will be plotted for all of the latency times.

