6.1 Changes from Protocol

There are no major discrepancies between protocol and SAP, only the following minor differences are described:

- 1. Population definitions (SCR, FAS, FAS-Cohort 1, and FAS-Cohort 2) added, the protocol specified the intent-to-treat population, however, the full analysis set will be used.
- 2. The unanticipated adverse device effects stated in the protocol removed from the analysis.
- 3. AEs leading to discontinuation of the investigational device removed from analysis, instead AEs leading to study discontinuation will be analyzed.

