9.2.3 Full Analysis Set

The **Full Analysis Set (FAS)** comprises all the detections of the wearable sensors done on the subjects who took at least 1 dose of MITs (Cohort 1) or Abilify MyCite (Cohort 2), excluding those detections with device malfunction (invalid session and impedance is bad).

For the primary endpoint in Cohort 1, the **FAS-Cohort 1** is a subset of the FAS and consists all the detections for subjects who took at least 1 dose of MITs (Cohort 1).

For the primary endpoint in Cohort 2, the **FAS-Cohort 2** is a subset of the FAS and consists all the detections for subjects who took at least 1 dose of Abilify MyCite (Cohort 2).

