10.6 Definition of Positive Detection Accuracy

The Positive Detection Accuracy (PDA) is defined as PDA = k/n, where *n* is the number of the total DOIs in FAS-Cohort 1 (malfunction sessions have been excluded from FAS-Cohort 1), and k is the number of total positive detections by the patch.

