12.3 Device Application

12.3.1 Directly Observed Ingestion

The following directly observed ingestion (DOI) data for Cohort 1 will be summarized in Table together with positive detection (Section 12.5.1) and latency data (Section 12.5.2) for the FAS-Cohort 1.

• Number of ingestions (15 times; 14 times; 13 times; 12 times; 11 times; 10 times; 9 times; 8 times; 7 times; 6 times; 5 times; 4 times; 3 times; 2 times; Once)

Furthermore, the above information will be provided in a listing based on **FAS-Cohort 1** together with

- The reason if subject does not ingest the miniature IEM tablets
- Date of ingestion
- Time of each ingestion,
- Volume of water (mL) ingested with placebo,
- Detection data
 - Patch serial number
 - Detected (True/False)
 - Patch impedance good (True/False)
 - Valid session (True/False)
 - Invalid session description
 - False positive (True/False)
- Latency data
 - Patch serial number
 - Date and time of detected
 - Date and time displayed
 - Patch detection latency (seconds)
 - Ingestion data transfer latency (seconds)
 - Total detection latency (seconds)
- Did the subject complete all the ingestions
- Was the subject discontinued from completing all ingestions and the reason for discontinuation

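### Device malfunctions that the SAP excludes from the PDA denominator have no reporting route in the protocol and appear in no planned table

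*Protocol*

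**What the plan says.** **Protocol, reporting.** Section 8.7.4, headed "Medical Device Incidents (Including Malfunctions", contains only the statement that it does not apply. Section 6.2.5 limits product quality complaints to Abilify MyCite tablets and adds: "PQCs will not be reported for the D-Tect Prototype Patch, MIT dose form, or app". Immediate reporting under 8.7.1 and 8.7.3 covers SAEs.

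**Protocol, endpoint.** Section 9.4.1 defines PDA as k ÷ n, where n "is the number of the total DOIs, and k is the number of positive detections by the patch". It makes no exclusion.

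**SAP, analysis set.** Section 9.2.3 builds the full analysis set "excluding those detections with device malfunction (invalid session and impedance is bad". Section 10.6 repeats this for the PDA denominator: "malfunction sessions have been excluded from FAS-Cohort 1".

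**SAP, changes from protocol.** Section 6.1 opens with "There are no major discrepancies between protocol and SAP, only the following minor differences are described" and gives three items. The malfunction exclusion is not one of them.

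**SAP, outputs.** The Cohort 1 listing in 12.3.1 has per-DOI fields that include "Patch impedance good (True/False", a valid-session flag and "Invalid session description". It is based on FAS-Cohort 1. The Cohort 2 listing in 12.3.2 has the patch serial number and latency data, but no impedance or validity field. The PDA summary in 12.5.1 gives the number of positive detections, PDA and its confidence interval.

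**The concern.** The D-Tect Patch is a new-generation, battery-powered device, and whether it registers ingestions is the primary question. The protocol treats its malfunctions as outside the trial, while the SAP expects them and acts on them in the primary analysis. These positions need to be reconciled.

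Followed as written, the rules let a DOI be classed as a malfunction and leave both the analysis set and the denominator without any planned table saying how many DOIs went that way or why. Protocol 8 (Testing Visit) adds to this. When a registration is missing, the team may change the patch, open a new bottle, have the system tested independently, and enrol more subjects to replace lost ingestions. That text asks for no record or tally of these actions.

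A reader of the results could not then tell a PDA achieved with no malfunctions from one achieved after several were removed. Because the target is a lower confidence limit above 95%, a single DOI can decide which side the result falls on.

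**Working it through.** **Inputs.** Cohort 1: 24 subjects × 15 DOIs = 360 (Protocol 9.1). Assumed PDA: 97.3% (Protocol 9.1). Target: lower limit above 95% (Protocol Table 3-1). Method: 95% Clopper-Pearson (Protocol 9.4.1), taken as two-sided. Planned patched subjects: 24 + 30 = 54.

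**Formula.** Lower limit = the 0.025 quantile of Beta(k, n − k + 1). All figures treat DOIs as independent.

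**The plan's own figure.** Protocol 9.1 puts the lower bound at 95% for a PDA of 97.3%.
- Expected detections: 0.973 × 360 = 350.28, lower limit 95.05%.
- At k = 350: 94.95%. At k = 351: 95.31%.

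The stated figure reproduces. It also shows that with 360 DOIs the target needs at least 351 detections, that is, at most 9 misses.

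**Effect of the exclusion.** The documents give no malfunction rate, so the number m of malfunction DOIs is varied. Assumptions: 9 misses in valid sessions, and all m malfunction DOIs undetected. Then k = 360 − 9 − m. The SAP rule divides by 360 − m and the protocol rule by 360.

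| m | SAP rule | Lower limit | Protocol rule | Lower limit |
|---|---|---|---|---|
| 0 | 351/360 | 95.31% | 351/360 | 95.31% |
| 1 | 350/359 | 95.29% | 350/360 | 94.95% |
| 5 | 346/355 | 95.24% | 346/360 | 93.56% |
| 10 | 341/350 | 95.17% | 341/360 | 91.88% |
| 15 | 336/345 | 95.11% | 336/360 | 90.24% |

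From m = 1 the two rules give opposite answers on the target. The row m = 15 is one patch failing for all of a subject's DOIs: 15/360 = 4.2% of the planned total. One failed patch is 1/54 = 1.9% of planned patched subjects.

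**Where an excluded DOI could be seen.**
- Incident report: none (Protocol 8.7.4).
- Complaint: none for patch, MIT or app (Protocol 6.2.5).
- Disposition table (SAP 12.1): subjects per analysis set, with no DOI counts and no malfunction reason.
- DOI summary (SAP 12.3.1): number of ingestions per subject, on FAS-Cohort 1.
- PDA table (SAP 12.5.1): no count of exclusions.
- Cohort 1 listing (SAP 12.3.1): has the right fields, but is based on the set after exclusion.
- Cohort 2 listing (SAP 12.3.2): no validity or impedance field.

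**The case against.** A reader might infer that failures of the device are counted nowhere. The documents do not support that. The failure that matters most, not registering an observed ingestion, is the primary endpoint. Undetected DOIs outside the exclusion stay in n and lower PDA, and SAP 10.7 censors them at the maximum observation time in the Kaplan-Meier analysis.

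Nor is data capture absent. For Cohort 1 the SAP holds impedance, session validity, a description and the patch serial number for each DOI. A True/False validity flag has little purpose if every invalid row is meant to be missing, so the authors may have intended a wider listing. SAP 9.2.3 joins its two conditions with a conjunction. If both are required, records meeting only one remain in the set and are listed.

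Some traces would also survive. Total DOIs are on the eCRF (Protocol 8.10.1), so exclusions in Cohort 1 could be found by subtraction. In Cohort 2, losing a subject's only DOI might show as a gap between analysis-set counts. Used patches return to the sponsor (Protocol 6.2.4), and Abilify MyCite tablet problems can be reported as complaints.

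Excluding poor contact can itself be defended, because Table 3-1 states the PDA target for a subject wearing the patch.

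All of this narrows the point without removing it. Subtraction gives a number without a cause, and no output plans it. The listing's stated basis still omits the excluded rows, and a defensible exclusion still needs to be counted.

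**Conclusion.** The point holds in a limited form. Malfunctions that the SAP excludes have no reporting route in the protocol and no place in any planned table. Read literally, they are also absent from the Cohort 1 listing, and Cohort 2 has no field for them. It is worth fixing because the excluded DOIs can decide the primary result: in the illustration, one of them moves the lower limit from 94.95% to 95.29%, across the 95% target.

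That size rests on assumptions: 9 other misses, excluded DOIs undetected, and DOIs independent. A bad-impedance DOI that was detected would change the figures. The documents give no malfunction rate, so the table shows what could happen and does not forecast it. The 15-DOI case is a worst case, since it needs a patch that fails from the first dose and is not changed, although Protocol 8 provides for changing it.

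A reader might also infer that the outputs would show zero malfunctions, that the protocol breaches a duty to report malfunctions that caused no harm, or that the complaint scope in 6.2.5 is wrong. The documents establish none of these. The outputs are silent and do not report zero. The documents set no duty to report harmless malfunctions. Limiting complaints to the Abilify MyCite tablets is a scope choice.

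**What to change.** **Protocol.** Reconcile 8.7.4 with SAP 9.2.3. Replace the not-applicable entry with a requirement to record each malfunction of the patch, app or phone on the eCRF (patch serial number, time, type, and action taken, including any patch change under the Testing Visit text) and to notify the sponsor. The complaint scope in 6.2.5 can stay as it is.

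**SAP.**
- Run the detection and validity listing of 12.3.1 on all DOIs of all patched subjects, with the same fields for Cohort 2.
- Add a table of malfunctions and excluded DOIs by reason and cohort, per subject and per DOI, placed beside the PDA result. A reader can then recompute PDA with all DOIs in the denominator.
- While the SAP is open, state in 9.2.3 whether one condition or both define a malfunction, and add the exclusion to the list in 6.1.

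**Cost.** A protocol paragraph, one short eCRF record, one table, and one listing on a wider basis. In a single-centre trial with one testing day per subject the site burden is small. The patch serial number is already on the eCRF, and the Cohort 1 validity fields already exist.
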